6 STUDY PROCEDURES

6.1 Schedule of Evaluations

Assessment	Screening: ONLINE/ PHONE	Baseline, Enrollment, Randomization: Visit 1 (Day 0)	AM Visit	PM Visit
Safety Inclusion/Exclusion Criteria Screening Survey	X			
Depression Inventory (PHQ-9)	X			
Edinburgh Handedness Inventory	X			
Morningness-Eveningness Questionnaire		X		
Subject Information Form (Demographics, Medical History)		X		
Arousal Rating		X	X	X
Substance Use Survey		X	X	X
Shipley Assessment (verbal only)		X		
Sleep Diary		X	X	X
Post-tDCS Application Survey			X	X
Baseline Post-Rest Survey		X		
Post-Experiment Survey			X (if final session)	X (if final session)
Consent Form		X		
Montreal Cognitive Assessment		X		
Debrief Form			X (if final session)	X (if final session)
Cognitive Tasks		X	X	X
Actigraphy		X	X	X
tDCS Stimulation (active or sham)			X	X

-
-

Adverse Events Questioning			X	X
---	--	--	---	---

6.2 Description of Evaluations

Cognitive Tasks:

Episodic Memory Task. We will cross stimulus type (words vs. pictures) with a recollection difficulty manipulation (items studied once or twice), all within-subjects. For the picture study list, participants will study words followed by a corresponding picture of the object (half colored pictures, half line drawings). Participants will decide if each picture is high or low detail, thereby drawing attention to perceptual features. For the word study list, participants will see the names of common objects and will be prompted to make one of two semantic judgments (Made in a factory? Found in house?), thereby drawing attention to conceptual features. We will give two recollection tests alternating across mini-blocks to avoid order effects. On the picture test blocks, verbal labels for the studied pictures will be intermixed with non-studied items, and participants will make one of three response options (studied as color, line, or new) followed by a confidence judgment. The structure of the word test blocks will be similar, whereby participants will make one of three response options (studied with a factory judgment, a house judgment, or new) in addition to the confidence judgment. Within each test, the items studied in the two different picture formats (or semantic judgments) will be matched on familiarity, so that participants will need to use recollection to make source judgments. Although pictures are typically better recollected than words, we have found that discriminating between these two different picture formats (namely, color or line judgments during the picture test) and these two different semantic judgments (namely, factory or house judgments during the word test) can be matched on difficulty with the repetition manipulation (i.e., comparing once-presented pictures to repeated words, Sarfan et al., 2014), allowing us to disentangle material-specific effects from recollection difficulty. Our primary dependent variable (DV) will be source recollection accuracy (the proportion of studied items attributed to the correct source, minus the proportion of non-studied items incorrectly attributed to that source). During each experimental session, subjects will perform the episodic memory task followed by the working memory task (described below).

-
-

Working Memory Task. Similar to the episodic memory task, the working memory task will involve a stimulus manipulation (verbal vs. visuospatial working memory) as well as a difficulty manipulation, all manipulated within-subjects and across mini-blocks to control for order effects. Specifically, we will use the N-back task with a verbal version (i.e., presenting the numbers 1-9 in a varied sequence) and a matched visuospatial version (i.e., presenting a colored square in one of 9 locations on a 3x3 grid in a varied sequence). Based on neuroimaging work, both tasks rely on bilateral PFC regions, but the former relies more heavily on left PFC, and the latter more heavily on the right PFC (for meta-analysis, see Owen et al., 2005). Difficulty will be manipulated by varying the N in the N-back task into “easy” and “difficult” versions for both younger and older adults (1 and 2 back for older adults, 2 and 3 back for younger adults). Our primary DV will be proportion of targets correctly identified minus the proportion of lures incorrectly endorsed.

6.2.1 Screening Evaluation

These evaluations occur to determine if the candidate is eligible for the study. Screening evaluations to determine eligibility must be completed within 3 months of study participation.

Consenting Procedure

The Study Coordinator will oversee the recruitment and screening procedures. Participants will have the option to complete the screening procedure via phone interview or an online questionnaire, as listed in the study advertisements. The screening procedure will start by obtaining informed consent for the screening procedures (verbal consent for phone, electronic for online), and then ask questions to verify that inclusion/exclusion factors are met, as well as describe the overall procedures of the study to determine eligibility and willingness.

Signed informed consent for the 3-session experiment will be obtained in person, during the first session in the lab (orientation/baseline day). Signed consent forms will be kept under lock and key in the [name] lab.

6.2.2 Enrollment, Baseline, and/or Randomization

Enrollment & Randomization

Enrollment begins when the participant signs the informed consent form for the 3-session experiment, at the start of the first lab session (i.e., baseline/orientation day).

-
-

After successful screening, participants will be randomized to either the AM-session-first condition or to the PM-session-first condition using the AM/PM Randomization REDCap database. Just prior to the baseline session, the participant will be assigned to a cognitive task condition using the Task Condition Randomization REDCap database. Finally, just before the first tDCS session, the participant will be assigned to a Soterix stimulation code, and to an electrode placement (either PFC or parietal), using the Participation REDCap database.

Baseline Assessments

During baseline assessment participants will complete cognitive tasks, demographic information, and other forms (Table 6.1).

[Morningness-Eveningness Questionnaire](#) (MEQ) *online survey* - Participants will take the MEQ, assessing AM and PM testing preferences, which is correlated with physiological measures of circadian rhythms and predicts time-of-day effects on cognitive tasks in younger and older adults (Horne & Ostberg, 1976; see May & Hasher, 2017). Younger adults are expected to express at least a mild preference for PM testing (approximately 70% of younger adults in our prior sample), and older adults at least a mild preference for AM testing (typically 75% of older adults, see Yoon et al., 1999). (See Appendix).

[Actigraphy and Sleep Diary](#) *online survey* - During the initial orientation session participants will be equipped with an actigraphy watch and instructions for this and the sleep diary, and these data will be collected over a minimum 7-day period. During this period, participants will return to the lab for 2 testing sessions (AM/PM, nonconsecutively), returning the actigraphy watch and sleep diary on the final testing session. These measures will be used to help interpret the differential time of day effects (AM vs PM) on cognitive functions that we predict in younger and older adults, as well as the predicted interaction with tDCS brain stimulation.

[Cognitive Tasks](#) *computerized tasks* - During the orientation session participants will take baseline cognitive tasks (without tDCS), thereby providing baseline measures for some of our analyses and also providing task-initiation practice during this baseline stage of the task, thereby minimizing the likelihood that such task-initiation effects would impact the subsequent AM/PM testing sessions (i.e., creating practice in the first part of the experiment in order to reduce such practice effects between the subsequent AM and PM testing sessions). See description above for more information.

-
-

Montreal Cognitive Assessment, *paper/pencil test* - We administer the Montreal Cognitive Assessment in order to exclude individuals that score outside the range for normal aging according to the recent meta-analysis of MoCA's ability to differentiate normal aging from MCI in Carson et al. (2018, Int. J of Geriatric Psychiatry).

Shipley Assessment (verbal only) *online survey* - During the second visit only, participants are given the verbal portion of the Shipley to test cognitive ability.

Substance Use Survey *online survey* - Subjects will be asked not to consume more than twice the amount of caffeine and nicotine they normally consume 4 hours prior to each session, and not to consume more than twice the amount of alcohol they normally consume 24 hours prior to each session, and we have them record their substance use in this survey (See Appendix).

Subject Information Form *online survey* - Questions regarding demographic information and medical history.

Baseline Post-Rest Survey *online survey* - Participants are asked about what was on their mind during a rest period, to determine if some participants intentionally review studied items prior to the memory test.

Arousal Rating *online survey* - Participants are asked about their alertness level before the encoding portion of the cognitive task and after a rest period.

6.2.3 Follow-up Visits (AM and PM Visits)

All participants will be enrolled in the baseline/orientation session, and they then will be assigned to active (or sham) tDCS for two follow-up experimental sessions, one in the AM and one in the PM.

- The time between each session will be at least 48 hours (i.e., at least 1 day intervening), thereby ensuring at least 1 full day of actigraphy data collected outside the lab prior to each tDCS session.
- The time between the baseline/orientation session and the final tDCS testing session should be no less than 7 days and no more than 12 days, thereby obtaining at least 7 days of actigraphy data and also providing some flexibility in the scheduling of the final session.

Follow up Assessments

Measures will include cognitive tasks, actigraphy, and the questionnaires listed in table 6.1.

-
-

Substance Use Survey See description above.

Arousal Rating *online survey* - Participants are asked about their alertness level before the encoding portion of the cognitive task adn before and after tDCS stimulation.

Post-tDCS Application Survey *online survey* - Participants report sensations during tDCS stimulation as well as what was on their mind during the stimulation.

Cognitive Tasks *computerized tasks* - See description above.

Adverse Events Questioning *verbal report* - Participants are asked if they have experience any after the baseline session. Responses are recorded in the Adverse Events Survey (see List of Administrative Logs).

6.2.4 Completion/Final Evaluation The final experimental session will be the final evaluation, and at the end of this session participants will complete a Post-Experiment Survey and finally receive a debriefing.

Post-Experiment Survey *online survey* - Participants report their sensations during the tDCS procedure, their expectations as to whether and how tDCS impacted performance, and also whether and how they believed they performed during the AM and the PM testing sessions.

Debrief Sheet *paper info sheet* - Participants are given an information sheet about the purpose of the study, which includes information about the stimulation and sham conditions (but not their own assignment), as well as hypotheses for AM and PM testing.

The debriefing sheet also will include citations for further reading. (See Appendix). *About Early Termination:* Participants have the right to end their participation at any time. In addition, the PI may terminate participation if a participant is in obvious non-compliance with the study procedures (e.g., responding randomly or sleeping during the cognitive task) or shows signs of moderate or severe adverse events associated with the study procedures (e.g., excessive discomfort with the tDCS electrodes).

-
-

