3 STUDY DESIGN

- Study Design: Double-blind, sham-controlled, age group x time-of-day tDCS study, with secondary analyses on sleep data, within-subjects baseline, and left parietal (younger adults only)
- Study Arms: 50 YA (active frontal), 50 YA (active parietal), 50 YA (sham: 1/2 prefrontal, 1/2 parietal), 50 OA (active frontal), 50 OA (sham: all frontal)
- Study Location: [name] Memory Lab, Department of Psychology, University of Chicago, Hyde Park Campus.
- Each participant ideally enrolled for 7 days (with flexibility up to 12 days), depending on scheduling constraints
- Intervention: 20 minutes of tDCS to prefrontal or parietal scalp locations, once during the AM (8 or 9am) and once during the PM (3 or 4 pm)
- Randomization and double-blinding separately for each age group

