4 SELECTION AND ENROLLMENT OF PARTICIPANTS

Inclusion and Exclusion Criteria

Participants must meet all the inclusion criteria to participate in this study, and candidates meeting any of the exclusion criteria will be excluded from study participation:

4.1 Inclusion Criteria:

- Right-handed (according to the [Edinburgh Handedness Inventory](#))
- Normal or corrected vision
- Fluent in English (started learning by age 6)

○
○

- Ability to understand and provide informed consent for study procedures, and to comply - with study procedures for the entire length of the study.
- For individuals in the ‘younger adults’ group, must be between 18 and 30 years of age
- For individuals in the ‘older adults’ group, must be between 60 and 75 years of age
- For individuals in the ‘older adults’ group, a score of 23 or above on the Montreal Cognitive Assessment (out of 30, education-corrected) is required. This is to minimize the inclusion of suspected mild cognitive impairment (MCI) or dementia, targeting individuals that score in the normal range according to the recent meta-analysis of MoCA’s ability to differentiate normal aging from MCI in Carson et al. (2018, Int. J of Geriatric Psychiatry).
- Performance above threshold on the episodic memory task during the baseline session. The threshold is defined as having a hit rate that is at least 5% greater than the false alarm rate, where hit rate is defined as the number of studied items identified as studied, divided by the total number of studied items, and false alarm rate is defined as the number of new items identified as studied, divided by the total number of new items. We don’t anticipate this threshold to exclude many, if any subjects.

4.2 Exclusion Criteria:

- Neuropsychological conditions associated with cognitive decline or seizure
- Cochlear implants or metal in the brain/skull (except titanium)
- Psychoactive medications or psychotic diagnoses
- History of excessive use (clinically treated) alcohol or narcotics
- Hospitalization for head trauma (e.g. concussions) in the past 5 years
- Individuals above a threshold score on an assessment of depression, specifically, a score of 10 or above on the PHQ-9 (Manea et al., 2012)
- Risk of pregnancy
- Low tolerance of skin irritation
- Prior brain stimulation experience (self-report)

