Power analysis: Our power analysis was based on our most recent and largest tDCS experiment with younger adults (Wong et al., in press, $n = 30$ per each between-subjects condition), which yielded a 12% difference in word test accuracy between sham (.23, $SD = .21$) and active tDCS (.35, $SD = .21$) in the 9 AM group, predicting that we would need 50 participants in each stimulation group in order to obtain a similar effect size (Cohen's $d = .57$, or a medium effect size) with 80% power at $p < .05$ (2 tailed, calculated with G-Power, v. 3.1.9.3). We therefore plan to test 50 younger adults and 50 older adults in each stimulation condition in order to detect effects of this magnitude. These sample sizes are considerably larger than most (if not all) of the between-subjects tDCS experiments on episodic memory published as of 2017. A sample size of 50 per condition also should yield sufficient power to detect the 2x2 interaction between brain stimulation (between-subjects) and time-of-day (within-subjects) in each age group, if we assume a similar effect size (partial eta squared = .06) for the interaction between time-of-day and stimulation we had obtained in younger adults in Wong et al. (in press), and also a .25 correlation between the repeated measures during AM and PM (80% power, alpha = .05).

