10.3.3 Metrics

Quality control metrics for outcome measures will be finding the expected effects of age-group (younger > older) on episodic memory (recollection) accuracy and working memory accuracy.

Moreover, for each participant, we expect hits to be greater than false alarms on these tasks. These and other aspects of quality and compliance (study forms, actigraphy) will be monitored by the Study Coordinator and PI.

-
-

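### Undefined removal for random responding after stimulation is assigned, combined with completers-only analysis and replacement, can pull a true tDCS benefit toward zero

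*Protocol*

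**What the plan says.** **Stopping participation.** Under the early-termination text in section 6.2.4, the principal investigator may end participation if a "participant is in obvious non-compliance with the study procedures (e.g., responding randomly or sleeping during the cognitive task"). There is no numeric definition and no requirement for evidence other than the responses themselves.

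**Timing.** Sections 5.2 and 6.2.2 assign the stimulation code just before the first tDCS session. A stop at the AM or PM visit is therefore after randomisation.

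**Consequence.** Section 5.4 restricts the primary analyses to participants with all three sessions. Section 8 replaces anyone who does not complete both experimental sessions with a new person in the same condition.

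**Visibility of scores.** Section 9.2.1 gives the research team access to all data except the stimulation codes. Section 10.1 lets the principal investigator see de-identified data during the study. Section 10.3.3 says that "for each participant, we expect hits to be greater than false alarms on these tasks" and has this monitored as an aspect of quality and compliance. It attaches no action to a failure.

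**Outcome.** The SAP (Set 1, analysis 1.a) defines memory performance as target hits less false alarms. Protocol section 6.2 defines the episodic outcome as source accuracy corrected for false attributions.

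**Baseline screen.** Section 4.1 sets an accuracy threshold at the baseline session: "The threshold is defined as having a hit rate that is at least 5% greater than the false alarm rate". This comes before code assignment.

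The SAP text provided contains no all-randomised analysis set, no rule for excluding data for non-compliance and no sensitivity analysis for such removals.

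**The concern.** Random responding gives an expected score near zero on a hits-minus-false-alarms scale, which is also where genuine poor performers lie. A judgement of random responding that leans on the score is therefore related to the outcome, and the completers-only rule turns a stop into an exclusion.

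If tDCS raises accuracy, fewer active than sham participants score near zero. A rule applied identically in both arms then removes more sham participants, raises the sham mean more and narrows the contrast. Blinding does not prevent this, because the imbalance comes from the scores and not from knowledge of the arm.

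The trial is presented as a replication attempt, so a contrast pulled toward zero could be read as a failure to replicate. The SAP also tests subgroups only after a significant overall test, so lost power carries forward.

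**Working it through.** **Inputs.** From the power analysis in protocol section 9.2: word-test accuracy in younger adults "between sham (.23, $SD = .21$) and active tDCS (.35, $SD = .21$) in the 9 AM group"; "with 80% power at $p < .05$ (2 tailed, calculated with G-Power, v. 3.1.9.3"); "we would need 50 participants in each stimulation group"; and "a .25 correlation between the repeated measures during AM and PM". Half of participants have the AM session first (counterbalanced). Assumptions not in the documents: normal scores; removed participants replaced up to 50 per arm; the share of low scorers removed, shown as a range; the same sham mean AM and PM; and a PM effect of either 0 or 0.12.

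**1. The plan's own figure.** d = 0.12/0.21 = 0.571. Normal approximation: n = 2(1.960 + 0.842)²/0.571² ≈ 48.1, so 49. The t-test needs 49.05, so 50. Power at 50 per arm is 0.81. The stated sample size reproduces.

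**2. Scores at or below 0.** Sham: Φ(−0.23/0.21) = Φ(−1.095) = 13.7%. Active: Φ(−0.35/0.21) = Φ(−1.667) = 4.8%.

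**3. Shift from removing all of them in the analysed session.** The retained mean is μ + σφ(μ/σ)/Φ(μ/σ).
- Sham: 0.23 + 0.0533 = 0.2833.
- Active: 0.35 + 0.0219 = 0.3719.
- Difference 0.0887, a loss of 26%; d = 0.49; power 0.68.

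**4. Removal after the first tDCS visit only.** This is closer to how a stop works, since it matters mainly for people with a session still to come. AM-first participants are selected on the AM score itself. PM-first participants are selected on the PM score, which moves their AM mean by only 0.25 of the PM shift.
- Sham: 0.23 + 0.0533 × (1 + 0.25)/2 = 0.2633.
- Active, PM effect 0.12: 0.35 + 0.0219 × 0.625 = 0.3637. Difference 0.1004.
- Active, no PM effect: AM-first mean 0.3719 (share kept 0.952) and PM-first mean 0.35 + 0.25 × 0.0533 = 0.3633 (share kept 0.863). The weighted mean is 0.3678. Difference 0.1045.

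A simulation with 2 million per arm agrees to within 0.0005. Its results, with ranges across the two PM assumptions:

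| Share of scores ≤ 0 removed after first tDCS visit | AM difference | Power, 50 per arm |
|---|---|---|
| None | 0.120 | 0.81 |
| 25% | 0.116–0.117 | 0.79–0.80 |
| 50% | 0.111–0.113 | 0.77–0.78 |
| 100% | 0.100–0.105 | 0.72–0.76 |

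For the average of the two sessions, full removal takes a true 0.060 (no PM effect) to 0.050, and a true 0.120 (same PM effect) to 0.100.

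**5. Higher-scoring measure.** With the same SD and difference but a sham mean of 0.40, full first-visit removal costs 4–5% (power 0.78–0.79). With a mean of 0.50 it costs about 2% (power 0.80).

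**6. When there is no harm.** With no true effect both arms lose the same share, the difference stays at 0 and the type I error is not inflated. If a share r in each arm truly responds at random, keeping them gives 0.12(1 − r), which is 0.118 at r = 2% and 0.108 at r = 10%. Removing them gives 0.12.

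**The case against.** A reader might infer four stronger things. The documents do not support them.

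- **That failing hits above false alarms is a ground for removal.** Section 10.3.3 states an expectation with no consequence, beside another expected finding (younger above older) that plainly removes nobody. Section 6.2.4 covers only obvious non-compliance, gives behaviours as examples and sets no score cutoff. The link between the two sections is an inference. The removal route does not need it, because section 6.2.4 names random responding itself.
- **That the monitored score is the outcome.** The SAP wording matches it, but the protocol's episodic outcome is source accuracy. Someone who recognises items and guesses the source scores about half of item hits minus false alarms. If 0.23 is source accuracy (an assumption), the item score could be as high as about 2 × 0.23 = 0.46, and far fewer people would fall near zero.
- **That the loss is 26%.** This needs every score at or below 0 in the analysed session to be removed. No section deletes a completed three-session record on its score. The baseline threshold should also thin the lower tail, and the figures above do not credit it.
- **That the effect must shrink.** Shrinkage needs both a true benefit and genuine low scorers mistaken for random responders.

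These points limit the size and the certainty. What remains is that the criterion is undefined, can be applied after randomisation, and leads to exclusion through sections 5.4 and 8. A score alone cannot separate a random responder from a genuine poor performer.

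**Conclusion.** The concern holds as a conditional bias toward zero, and it does not depend on unblinding. On the planning figures, removal after the first tDCS visit costs about 3% of the AM difference if a quarter of scores at or below 0 are removed, 6–7% if half are, and 13–16% if all are. Planned power is only 0.81, so on these figures a moderate removal rate already takes it to or slightly below the 0.80 target. The loss is smaller if the monitored score runs higher, and 26% is an extreme case.

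This rests on normal scores, on word-test figures for younger adults in the morning, and on an unstated removal rate. The documents give no score distribution for older adults or for item hits minus false alarms. The baseline threshold is not part of the problem, because it acts before stimulation is assigned.

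**What to change.** The change is to the analysis only. The principal investigator's discretion to stop participation is untouched.

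- Amend sections 5.4 and 8 and the SAP so that everyone who was assigned a code and received stimulation contributes their available sessions to the primary mixed model. Replacement may still fill places, but it should not delete the data of the person replaced.
- State that, after code assignment, accuracy alone does not remove data from the primary analysis. A sentence in section 10.3.3 alone would not be enough, because sections 5.4 and 8 would still drop anyone who was stopped.
- Define any data exclusion for non-compliance before unblinding, on evidence other than the score.
- Report terminations and their reasons by arm.
- Give the completers-only version without suspected random responders as a sensitivity analysis.

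The cost is a few sentences. The downside is that a few true random responders stay in the primary analysis, which by step 6 would dilute a difference of 0.12 to 0.118 if they were 2% of each arm and to 0.108 if they were 10%.
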